13.2 Secondary Endpoints

Continuous secondary endpoints (other than the neuroimaging outcomes) will be analyzed using random coefficient regression models similar to the one defined above for the primary outcome variable. In addition, analyses using MMRM will be conducted as well, in order to estimate the treatment differences separately at each visit. The neuroimaging outcomes will be analyzed by calculating AUC values and using ANCOVA models, similar to the primary analysis.

Categorical time-to-event endpoints (EDSS-plus) will be analyzed using Cox Proportional hazards models, with treatment group as a covariate. The patients who do not have an event during the study will be censored at the time of the last assessment of EDSS-plus. The exact number of days from the date of first dose to date of event or censoring will be used as endpoint.

The ITT population will be used for the analysis of the secondary endpoints.

14 Analysis of safety

The safety analyses will be conducted for the following study periods and treatment groups:

- Pre-treatment baseline phase: untreated patients, classified by the treatment group in the double-blind phase and overall
- Double-blind phase: Idebenone treated patients versus placebo treated patients

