11. STATISTICAL ANALYSIS

11.1 *Data acquisition and processing*

All clinical, neuroimaging volumetric and biomarker data will be collected sequentially and analyzed in a blinded fashion from coded samples. Data will be acquired prospectively and transcribed to the research database. For the imaging biomarker of ventricular volume the analysis will be performed only after completion of baseline or treatment periods, because the images need to be co-registered to the first acquired image. For biomarker data that can be acquired from cryopreserved biological samples, baseline and treatment data points will be evaluated simultaneously, to limit effect of inter-assay variation. Every effort will be made to have single rater/investigator to acquire one type of quantifiable clinical, neuroimaging and biomarker data for the entire cohort. Codes will be broken only after all pre-specified quantifiable data constituting primary and secondary outcomes are collected and recorded in the database.

11.2 *Statistical analyses of outcome measures*

Further details of the statistical analysis (e.g. definition of analysis populations) will be defined in a Statistical Analysis Plan which will be finalized before the database lock and opening of the treatment code.

Introduction

- a) For data collected only at 2 time-points (i.e. single collection during pre-treatment baseline and single collection at 1 year of therapy), such as CSF data, we will calculate for each individual %-change between baseline and therapy time-points
- b) For data collected every 6 months (i.e. clinical data and quantitative brain MRI data) we will calculate area under curve (AUC) for 3 data points obtained during pre-treatment baseline period and compare it to AUC for 5 data points obtained during the treatment period.

The rationale for using AUC (as opposed to linear regressions) is explained in detail in Figure 3:

[figure not shown]

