The imputed datasets generated with the approach described above do contain only non-missing values and are used as input in the model for the sensitivity analysis of the primary outcome variable. MMRM similar as described in Sensitivity Analysis 2 will thus be run on each of the 1000 generated imputed datasets and the difference between the treatment groups will be estimated. Finally, the results from these analyses will be combined to derive an overall estimate of the treatment difference. In addition to the estimates, corresponding 95% confidence intervals and p-values will be calculated.

4. Multiple Imputation assuming data missing not at random (MNAR) will be done to compare idebenone to placebo. Control group based assumption (Copy Reference imputation) will be used, i.e. the trajectories of the patients are assumed to follow the placebo group trajectories after the discontinuation. Methods similar to the procedure described above will be used to generate monotone missing data. After this, the missing data will be imputed sequentially for each visit (first Month 3, followed by all subsequent visits). Only the data from the control group (placebo group) will be used as input for each imputation of both treatment groups.

Secondary Endpoints

Continuous variables will be analyzed using random coefficient regression models and/or MMRMs similar to the one defined above for the primary outcome variable

Categorical Endpoints will be analyzed using cox proportional hazards models, with treatment group, baseline values (if applicable) and baseline age as covariates.

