This analysis was performed and published, including measurements of z-scores (*Kosa, Ghazali et al. 2016*). We have compared total of 58 clinical, imaging, electrophysiological and optical coherence tomography outcomes. In the first IPPOMS cohort (which ended up being 35 patients because we lost some MRI outcomes due to technical issues such as poor quality of scans and the protocol stipulated minimum of 30 patients per outcome) we observed that total of 15 outcomes reached statistical significance based on un-adjusted p-values (See Table 2 in the (*Kosa, Ghazali et al. 2016*)). We then validated these 15 outcomes for their ability to reliably detect yearly MS disease progression in 2 independent validation cohorts: IPPOMS2 cohort (n=34) and RIVITALISE cohort (n=29). Seven out of 15 outcomes validated statistically-significant change in both independent validation cohorts, when properly adjusting for multiple comparisons. Surprisingly, the default primary outcome for IPPOMS protocol, brain atrophy measured by SIENA methodology was not validated. While six MRI biomarkers (ventricular volume and 5 diffusion-tensor imaging [DTI] markers) validated statistically-significant change in both validation cohorts, our enthusiasm for these outcomes was lowered by observation that only one of them, ventricular atrophy, showed any correlation with clinical outcomes. This measure had mild correlation with 2 cognitive scales (PASAT and SDMT) and with a MS functional composite (MSFC) scale. However, this correlation was observed only in the cross-sectional paradigm, which benefited from a broad range of disabilities present in merged untreated progressive MS cohort (n=98). In contrast, we observed absolutely no correlation between any MRI outcome and any clinical measure in 1-year longitudinal paradigm – in other words, change on MRI biomarkers did not correlate with change in any clinical outcome. The article explains in length why this is so, documenting poor signal-to-noise ratio (SNR) of even best performing MRI biomarkers for the level of change observed in the 1-year longitudinal MS data in comparison to scan-re-scan variability observed in MRI technical controls (i.e. healthy donors scanned twice at each scanner).

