The AUC values will be calculated for both the pre-treatment baseline phase (from Months -12, -6 and 0) and for the double-blind phase (from Months 0, 6, 12, 18 and 24). For each of the AUC values, at least two valid CombiWISE scores during the phase in question are required. If less than two values AUC values are available for any of the two phases, the AUC score will be set as missing. In addition, if the first value of the phase in question is missing, the CombiWISE score will be set as missing.

Linear trapezoidal method will be used to calculate the AUC values. For each time interval (time between two visits), the AUC is calculated as $0.5 \times (Y_1 + Y_2) \times (t_2 - t_1)$, where Y_1 and Y_2 are the CombiWISE scores (as changes from baseline) at the beginning and end of the interval and t_1 and t_2 are the start and stop dates of the interval. The time will be converted to years (number of days divided by 365.25) for the AUC calculation. The baseline for the pre-treatment period is the visit scheduled at the beginning of the pre-treatment period (Month -12) and the baseline for the double-blind period is the visit at Month 0.

In case of intermittent missing data between two non-missing visits, the formula for linear trapezoidal method will be used as such. In case of premature discontinuations, the AUC values after the time of discontinuation will be set as missing.

After these calculations, the AUC values calculated for the different periods will be summed over the pre-treatment baseline phase (Month -12 to Month 0) and over the double-blind phase (Month 0 to Month 24). Because the follow-up times can vary from patient to patient, the AUC values will be made comparable by scaling them using the follow-up time. The scaling will be done by dividing the AUC value by the square of the actual duration of each of the phases. For the pre-treatment baseline phase, the AUC will be scaled as $AUC/[t_0 - t_{-12}]^2$, where t_0 and t_{-12} are the dates of visits at Month 0 and Month -12, respectively. For the double-blind phase, the AUC will be scaled as $AUC/[t_{last} - t_0]^2$, where t_{last} and t_0 are the dates of the last visit and the visit at Month 0, respectively. Similarly as above, the time will be converted to years. The scaled AUCs will be used in all statistical analyses.

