4.3 Secondary efficacy endpoints

All components of the primary endpoint will be analyzed as secondary endpoints:

- EDSS: the EDSS score (scored as 1.0, 1.5, ..., 10.0) is recorded as such and requires no derivation.

-
- SNRS: the SNRS score, which can range between 100 (normal status) and 0 (worst possible score) is recorded as calculated by the investigator.
 - 25 foot walk (25FW): 25FW is the average of two attempts of walk test. In case any of the two attempts is unsuccessful, 25FW will be set as missing. This endpoint will be primarily analyzed without any transformation to facilitate the interpretation, but in case the data are skewed, additional analyses may be conducted by log2 transformation of the average.
 - 9 hole peg test (9HPT) performed on non-dominant hand (NDH-9HPT): NDH-9HPT is the average of the two attempts on 9 hole peg test. In case any of the two attempts is unsuccessful, NDH-9HPT will be set as missing. This endpoint will be primarily analyzed without any transformation to facilitate the interpretation, but in case the data are skewed, additional analyses may be conducted by log2 transformation of the average. Furthermore, similar analyses will be conducted for data based on the dominant hand and the average of the non-dominant and dominant hands.

In addition, the following variables will be analyzed as secondary endpoints:

- Neuroimaging outcomes: Inhibition of individualized rates of enlargement of ventricular volume: enlargement of segmented volume of lateral and 3rd ventricles. This was the primary endpoint of the initial protocol version.
- EDSS-plus, as defined in (Cadavid, Cohen et al. 2017): EDSS-plus is defined as progression on at least 1 of 3 components (EDSS, 25FW, and/or NDH-9HPT) confirmed ≥ 24 weeks apart and with a $\geq 20\%$ minimum threshold change for 25FW and NDH-9HPT. As the visits in this study are scheduled to be conducted with 6 month intervals, a confirmation at the next scheduled visit is considered sufficient, even if the time between the visits would be less than 24 weeks due to visit scheduling.

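### Ventricular volume, a rate endpoint, is analysed only by an AUC anchored on the single Month 0 scan; this costs precision, by an amount the documents cannot fix, and better covariates recover part of it cheaply

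*SAP*

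**What the plan says.** SAP 4.3 defines the imaging secondary endpoint as "Inhibition of individualized rates of enlargement of ventricular volume: enlargement of segmented volume of lateral and 3rd ventricles". SAP 13.2 then divides the methods. "Continuous secondary endpoints (other than the neuroimaging outcomes) will be analyzed using random coefficient regression models similar to the one defined above", with MMRM added for visit-wise differences. For imaging, "The neuroimaging outcomes will be analyzed by calculating AUC values and using ANCOVA models, similar to the primary analysis".

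The AUC rule is in SAP 4.2: linear trapezoids on changes from baseline, divided by the squared duration of the phase, where "the baseline for the double-blind period is the visit at Month 0". By analogy with SAP 13.1.1, the covariates would be the pre-treatment AUC, the Month 0 value and age.

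The protocol points both ways. Its introduction to section 11.2 says "For data collected every 6 months (i.e. clinical data and quantitative brain MRI data) we will calculate area under curve (AUC", and section 11.3 gives an imputation rule for AUCs of MRI data. Its rule for secondary endpoints in section 11.2 reads "Continuous variables will be analyzed using random coefficient regression models and/or MMRMs".

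**The concern.** For a rate measured on evenly spaced scans, the least-squares slope spreads the weight over all of them. The AUC of change puts most of its weight on one scan. Month 0 volume as a covariate does not cure this, because between-patient spread in ventricular volume is expected to be far larger than scan error, so the covariate says little about the error in that scan.

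The loss is largest when scan noise is large relative to yearly change. Protocol 11.5 describes "poor signal-to-noise ratio (SNR) of even best performing MRI biomarkers" over one year. Ventricular volume is the only imaging secondary endpoint and the imaging part of the second primary goal (Protocol 5.2). CombiWISE has slope and MMRM sensitivity analyses beside its AUC; ventricular volume has no second analysis.

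**Working it through.** **Inputs from the documents.** Scans at Months -12, -6, 0, 6, 12, 18 and 24; the AUC rule of SAP 4.2; 33 per arm; two-sided 5%; linear progression within patient (SAP 3.2). **Assumed, because the documents give no variance for ventricular volume:** single-scan error SD s; SNR = mean yearly enlargement / SD of a scan-rescan difference (√2·s); CV = between-patient slope SD / mean slope; between-patient volume SD of 10 s.

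**1. The protocol's factor of 4.** For a linear change of b per year over T years, AUC = bT²/2. Two years give 2b and one year gives 0.5b, ratio 4, as the text to Protocol Figure 3 states. Under the SAP scaling, AUC/T² = b/2 in both phases. The scaled AUC therefore measures half the rate without bias.

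**2. Weights.** Trapezoids on change from Month 0 at 0, 0.5, 1, 1.5 and 2 years give (-1.75, 0.5, 0.5, 0.5, 0.25). Sum of squares: 3.0625 + 3 × 0.25 + 0.0625 = 3.875. Month 0 share: 3.0625/3.875 = 79%.

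**3. Error variance on the yearly-rate scale, independent errors.**
- Treatment-phase AUC: rate = AUC/2, so 3.875/4 = 0.969 s².
- Treatment-phase slope: Sxx = 1 + 0.25 + 0 + 0.25 + 1 = 2.5, so 1/2.5 = 0.400 s². Ratio 0.969/0.400 = 2.42.
- Pre-treatment AUC: weights (-0.75, 0.5, 0.25), sum of squares 0.875, times 4 = 3.5 s². Pre-treatment slope: Sxx = 0.5, so 2.0 s².
- Shorter follow-up narrows the gap: ratio 2.10 with the last scan at Month 18, 1.75 at Month 12, and 1.0 at Month 6 (8 s² each).

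**4. After ANCOVA.** For outcome weights q, covariate weights C and scan covariance Σ (random intercept and slope plus error), residual variance = q′Σq − q′ΣC′(CΣC′)⁻¹CΣq. Slope variance in units of s² is k = 2·SNR²·CV². Each method uses its own pre-treatment covariate plus Month 0 volume. Slopes are the same before and after Month 0, and errors are independent. Power is for a 50% slowing acting linearly.

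| SNR | CV | k | AUC/slope residual variance | Power, AUC | Power, slope |
|---|---|---|---|---|---|
| 0.5 | 0.5 | 0.125 | 2.17 | 28% | 52% |
| 1 | 0.5 | 0.5 | 1.63 | 65% | 85% |
| 1 | 1 | 2 | 1.43 | 43% | 57% |
| 2 | 1 | 8 | 1.53 | 81% | 94% |

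First row in full: residual variances 1.060 s² and 0.489 s². Mean rate 0.5 × √2·s = 0.707 s, so the effect is 0.354 s. Standard errors √(2 × 1.060/33) = 0.253 s and √(2 × 0.489/33) = 0.172 s. Noncentralities 1.40 and 2.05 give 28% and 52%. With volume SD from 5 s to 30 s the ratios hardly move; the range is 1.43 to 2.18.

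**5. Looser assumptions.** Pre/post slope correlation of 0 to 0.7, and errors correlated at 0.5 between adjacent visits, give ratios from about 1.04 (high SNR, unrelated slopes, correlated errors) to about 2.3 (low SNR, unrelated slopes, independent errors).

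**6. Another effect shape.** For a level shift d from Month 6 on, the AUC on the rate scale moves by (1.75/2)d = 0.875d and the slope by (0.2 + 0.4)d − 0.2d = 0.4d. Information: 0.875²/0.969 = 0.79 against 0.4²/0.40 = 0.40. The slope has 0.51 times the information of the AUC, so the ranking reverses.

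**7. AUC kept, three separate covariates.** Pre-treatment AUC and Month 0 volume are (with even spacing) two linear combinations of the three pre-treatment volumes. Entering all three therefore cannot raise the model's residual variance, apart from the 1 df. By the formula in step 4 it falls 34% at SNR 0.5 and 12% at SNR 1 (CV 0.5). In the first row, 1.060 × 0.66 = 0.70 s²; the standard error is √(2 × 0.70/33) = 0.206 s, noncentrality 1.72, power about 39% against 28%. At SNR 1, CV 1 the gain is nil. With errors correlated at 0.5 it is at most about 10% on this grid.

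**The case against.** The AUC is a reasoned choice. The text to Protocol Figure 3 speaks of outcomes collected every six months in general, with CombiWISE as the example. It argues that a slope ignores structural or functional repair appearing as a shift in level. Structural repair can include imaging, and step 6 confirms the point: for an early shift the AUC is clearly better. This stands, and it is why the slope should not displace the AUC as lead.

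The second argument there, that a three-point slope ignores the middle value, is correct as algebra (weights -1, 0, 1). It does not make the pre-treatment AUC more precise: 3.5 s² against 2.0 s².

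A reader might infer that imaging was singled out across the whole trial. It was not. The primary endpoint uses the same method, and Protocol 11.2 and 11.3 name AUC for MRI. The contrast is only with the other continuous secondary endpoints in SAP 13.2.

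The comparison also favours the slope by assuming a linear effect, independent errors and complete scans. Protocol 11.1 co-registers images to the first one acquired, so independent errors cannot be presumed. The ITT set in SAP section 8 needs only one post-baseline assessment; an unweighted per-patient slope would then mix error variances from 0.4 s² to 8 s².

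**Conclusion.** The point holds as a loss of precision. The exact parts are the 79% share of Month 0 and, for five complete scans with independent errors, the pure-error ratio of 2.42. The ratio after ANCOVA is not a property of this trial that can be read from its documents: it is 1.43 to 2.18 for SNR 0.5 to 2 and CV 0.5 to 1 with stable slopes and independent errors, and about 1.04 to 2.3 when those conditions are relaxed. The protocol's remark on poor signal-to-noise points towards the upper part but gives no figure for ventricular volume.

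Three stronger readings are tempting and not supported. The AUC is not biased for a rate, and no type I error problem follows; under linearity it is half the slope. A null imaging result is not thereby uninformative, since AUC power reaches 65% and 81% in some rows of the table. Nor is the slope better whatever the drug does, since an early level shift reverses the order. SAP 3.2 says the focus moved from MRI to clinical endpoints, and SAP section 9 calls the study exploratory, so this is a modest, low-cost improvement to a secondary analysis.

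**What to change.** In SAP 13.2, keep the ventricular AUC as the lead analysis. Replace the pre-treatment AUC and Month 0 volume with the Month -12, -6 and 0 volumes as three separate covariates, plus age. This uses all three pre-treatment scans, which the protocol wanted, and keeps the AUC's sensitivity to a level shift. It costs 1 df and a line of code. A missing Month -6 volume needs a stated rule; the adjacent-visit average in Protocol 11.3 would serve. Expected gain: residual variance about 34% lower at SNR 0.5 and 12% at SNR 1 (CV 0.5, stable slopes, independent errors), and little at higher SNR or with correlated errors.

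Also report, as supportive, the random coefficient slope model that SAP 13.2 already uses for the other continuous secondary endpoints. It weights unequal follow-up properly, which an unweighted per-patient slope does not.

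Protocol 7.6 states that the data analysis is complete. If these analyses are run now, they should be labelled as added afterwards and shown beside the pre-specified result.

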14.1 Disposition

Number of enrolled, randomized, completed and discontinued patients will be summarized. In addition, the reasons for discontinuations will be tabulated. The time to premature discontinuation will be illustrated with Kaplan-Maier plots.

14.2 Adverse events

All Adverse Events (AEs) will be coded using the Medical Dictionary for Regulatory Activities (MedDRA). The treatment-emergent AEs (i.e., events which start or worsen during the study treatment) will be tabulated by treatment group (when applicable), system organ class and preferred term. Both subject counts (number of patients reporting the event at least once) and event counts (total number of reported events) will be calculated. The percentages out of all patients will be calculated for the subject counts. In addition, incidence rates will be calculated by dividing the event count by patient years of exposure to the study treatment (double-blind phase) or by duration of follow-up (pre-treatment baseline phase).

In addition, the treatment-emergent AEs will be evaluated by severity grade and by relationship to the study treatment. The serious AEs will also be summarized.

15 Execution of statistical analyses

NINDS will be responsible for the final statistical analyses. Santhera Pharmaceuticals may support in conduction of the analyses, but in this case analyses have to be approved by the NINDS.

16 Changes in the planned analyses

This SAP defines the analyses planned in the protocol in more detail and introduces additional sensitivity analyses of the primary endpoint. In addition, the analyses of the secondary efficacy endpoints and safety data have been defined in more detail.

The following minor change was done for the analysis of the primary endpoint. The AUC values will be scaled to the duration of the assessment period, instead of using the calculated AUC values as such (and by dividing the double-blind period AUC values by 4). This change was done prior to unblinding of the study and was deemed as minor and not requiring a protocol amendment.

17 Hardware and software

Statistical analysis, tables and patient data listings will be performed with SAS[®] version 9.4 for Windows (SAS Institute Inc., Cary, NC, USA).

18 References

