9.1.16 Monitoring of adverse events

The patient will be instructed to contact the investigator immediately should the patient manifest any sign or symptom perceived as serious during the period extending from performance of the first study procedure (e.g. drawing of a blood sample) up to and including 1 month after the last dose (telephone interview at month 25). After this period of time, the patient should report to the investigator only adverse events that are serious and perceived as possibly related to their participation in this study.

Additionally, the patient will be instructed to contact the investigator immediately if he/she believes that he/she has fathered/conceived a child. Testing would be performed to verify that the subject or subject's partner was pregnant. If the pregnancy test were positive, the patient would be instructed to immediately stop taking the study drug and his/her treatment assignment would be revealed to the investigators and the DSMB. The patient or partner would be counseled and followed closely during the pregnancy by the NIH research team and would implement any recommendations made by the DSMB.

Patients will be physically examined by the investigator approximately every 6 months for the study duration. Extensive laboratory monitoring of the following will occur every 6 months for the study duration: CBC with differential, Chemistry panel 20, and urinalysis and pregnancy test (for females with childbearing potential). Additionally, laboratory monitoring (CBC, chemistry panel with liver function tests) will be performed every 3 months after initiation of dosing of idebenone for the first year of treatment and every 6 months thereafter.

All adverse events occurring within 1 month following the last administration of the study medication must be recorded on the Adverse Event Form irrespective of severity and seriousness, and whether or not they are considered related to the study medication. Additionally, all serious adverse events (SAE) brought to the attention of the investigator during the period starting from the day of performance of the first study procedure to the telephone interview on month 25, must be recorded and reported to the FDA in accordance with federal regulations and NIH procedures. Any SAE reported by the patient after month 24, will be subjected to expedited reporting only if judged to be related to the study treatment by the Investigator.

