4.1 Primary safety endpoints

The primary safety endpoints include premature discontinuations of study treatment, serious adverse events and all adverse events. For more details on the analysis of the safety data, see Section 12 of this SAP.

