- Duration of exposure (days): exposure to study treatment (idebenone or placebo), where the duration is calculated as date of last dose minus date of first dose during the double-blind phase. In addition, the duration of follow-up during the pre-treatment baseline phase will be calculated as date of first dose during the double-blind phase minus date of first visit (Month -12). The durations will be summarized with descriptive statistics separately for pre-treatment baseline phase and for the double-blind phase.
- Total exposure to study treatment, expressed as person years (sum of duration of exposure to study treatment over all patients in days divided by 365.25, classified by treatment group). The total exposure will be calculated for the double-blind phase and summarized by treatment group. For the pre-treatment baseline phase, the total follow-up time will be calculated similarly, and summarized by treatment group and overall.

13 Analysis of efficacy

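### Non-serious adverse events that start or worsen in the month after the last dose are collected but fall in no specified SAP table, and the window for the SAE summary is not stated

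*SAP*

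**What the plan says.** - **Collection.** Protocol 9.1.16: "All adverse events occurring within 1 month following the last administration of the study medication must be recorded on the Adverse Event Form", whatever the severity, seriousness or relation to study drug. SAEs are recorded from the first study procedure to the month 25 telephone interview. The protocol's section on individual subject withdrawal adds 2 months of follow-up for patients who stop dosing.
- **Endpoints.** SAP 4.1: "The primary safety endpoints include premature discontinuations of study treatment, serious adverse events and all adverse events".
- **Tables.** SAP 14.2 tabulates treatment-emergent events by arm, system organ class and preferred term, and defines them as "events which start or worsen during the study treatment". The severity and relationship summaries use the same events. On serious events it says only "The serious AEs will also be summarized".
- **Safety periods.** SAP 14 lists two: the pre-treatment baseline phase, and "Double-blind phase: Idebenone treated patients versus placebo treated patients".
- **Exposure.** In SAP 12, "the duration is calculated as date of last dose minus date of first dose during the double-blind phase". The double-blind incidence rates in SAP 14.2 divide event counts by patient-years of that exposure.
- **Precedence.** The SAP's opening section says that it prevails over the protocol where the two differ.

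**The concern.** Long-term safety is the first primary goal in both documents. The protocol sets one window for collecting adverse events, and the SAP sets a shorter one for reporting them. Because the SAP takes precedence, nothing in the protocol restores the missing month to the analysis.

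The days just after stopping are not obviously irrelevant. Protocol 4.5 gives a mean adult half-life of 12.7 hours for total idebenone in the repeated-dose study at 60 mg/kg, so five half-lives is 63.5 hours, about 2.6 days after the last dose. Safety laboratory tests are 3 to 6 months apart, so an abnormality in a patient who stops between visits may be first detected, and possibly dated, after the last dose. Under the SAP as written, part of a primary safety endpoint would be in the database and absent from the specified tables.

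**Working it through.** The documents state no figure on this point, so there is none to reproduce. The check has two parts.

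**1. Where would a post-dose event appear?** Take an event whose onset or worsening comes after the last dose but within 1 month of it.

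- Class and term tables (SAP 14.2): no, because it does not start or worsen during treatment.
- Severity and relationship summaries (SAP 14.2): no, for the same reason.
- Incidence rates (SAP 12 and 14.2): the denominator ends at the last dose, and no post-dose rate is planned.
- SAE summary (SAP 14.2): possibly, if the event is serious. The sentence is not limited to treatment-emergent events, but it gives no window and SAP 14 has no post-treatment period.
- Disposition (SAP 14.1): this shows that a patient stopped and why. It does not show a later event.
- General statement (SAP 9): data in the database will in general be summarised, but no adverse event table or window is named.

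A non-serious post-dose event therefore has no specified table.

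**2. How much time is uncovered?** Inputs: 66 treated patients (SAP 6.1), 24 months of treatment (SAP 3.1), 1 month of post-dose collection (Protocol 9.1.16). Assumption: all 66 complete 24 months.

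- On treatment: 66 × 24/12 = 132.0 patient-years.
- Post-dose month: 66 × 1/12 = 5.5 patient-years.
- Share: 5.5 / (132.0 + 5.5) = 5.5 / 137.5 = 4.0%.

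For one patient treated for m months, the share is 1/(m + 1). The stopping times below are illustrative, since the documents give no distribution of stopping times.

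| m (months) | Post-dose share |
|---|---|
| 24 | 1/25 = 4.0% |
| 12 | 1/13 = 7.7% |
| 6 | 1/7 = 14.3% |
| 3 | 1/4 = 25% |

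**Check on the remedy.** If post-dose events were added to the count while exposure still ended at the last dose, a constant event rate would be overstated by the factor (m + 1)/m: 25/24 = 1.042 at 24 months, 13/12 = 1.083 at 12 months and 7/6 = 1.167 at 6 months. Numerator and denominator must be widened together.

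**The case against.** The case for leaving the plan alone has several sound parts.

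- **An on-treatment window is defensible.** With a half-life of 12.7 hours, 30 days is 720/12.7, or about 57 half-lives, and Protocol 4.5 reports no relevant accumulation of metabolites. Most of the extra month is off-drug time and would mainly add background events. This stands as a reason to keep on-treatment tables. It does not justify leaving collected events untabulated.
- **The rates are coherent.** Count and exposure both stop at the last dose. The gap is in coverage, and no rate is miscalculated.
- **The wording is loose.** SAP 14.2 also plans rates for the pre-treatment phase, when no study drug is given. For patients who stop drug but stay in follow-up, study treatment could mean dosing or the whole double-blind phase. This shows a need for clarification more than a deliberate exclusion. Even on the wider reading, a completer's month 24 to 25 lies outside the double-blind phase.

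A reader might go further and infer that the tables lose the events that made patients stop, and so bias the comparison towards safety on idebenone. The documents do not support that. Events are classed by onset or worsening, so a symptom that began on drug and led to stopping is counted even if reported later. Premature discontinuation is itself a primary safety endpoint, with reasons tabulated and times plotted under SAP 14.1, so an imbalance in stopping would be visible. Nor can it be said that all post-dose events are lost, because the SAE summary may include serious ones.

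**Conclusion.** The point holds as a gap in coverage. Non-serious adverse events with onset or worsening in the month after the last dose are collected under the protocol and fall within a primary safety endpoint, yet no specified SAP table contains them. Whether post-dose SAEs are summarised cannot be settled from the text.

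The gap is about 4% of person-time under adverse event collection if all 66 patients complete 24 months. It is larger for any patient who stops early, by an amount that depends on stopping times the documents do not give. These are shares of time at risk, not of events or of bias. The direction of any bias between arms cannot be determined: it would require more early stopping, or more post-dose events, in one arm, and no counts by arm are given. This is a change worth making because it is cheap. It does not by itself undermine the safety comparison.

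**What to change.** Either of two changes closes the gap.

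1. Define treatment-emergent in SAP 14.2 as starting or worsening from the first dose to 1 month after the last dose, and use the same window for the patient-years in SAP 12 and 14.2.
2. Keep the on-treatment tables and rates, and add a by-arm table of events with onset or worsening within 1 month after the last dose.

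With either option, state the window for the SAE summary.

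No new data are needed, since the protocol already requires these events to be recorded. Both options bring in a few more background events in both arms. The first also changes the exposure denominator, so it takes more than one sentence. The second leaves the on-treatment rates undiluted. Protocol 7.6.10 records that data analysis is complete, so in practice the second option could be supplied as a supplementary table.
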